10.4. Recording Concomitant Medication

All concomitant therapies or procedures must be recorded on the subject's CRF according to instructions for CRF completion. The reason for initiation of such therapies or procedures must also be recorded on the CRF.

11. STUDY TREATMENT MANAGEMENT

Study site staff should review procedures for the handling and administration of DMF, montelukast, and placebo with subjects at the Randomization Visit, in addition to referring subjects to the relevant USPI for specific instructions on the handling, administration, storage, and preparation of study treatments.

11.1. Dimethyl Fumarate

Dimethyl fumarate will be obtained via commercial methods and should be handled, administered, stored, and disposed of according to the prevailing Package Insert. For further details on the DMF drug product, refer to the local USPI for more information.

11.1.1. Dimethyl Fumarate Accountability

Subjects are to be instructed to bring all unused DMF to the study site. The site will perform and document accountability based on the DMF that the subject presents at the study visits.

11.2. Montelukast and Placebo

Montelukast and placebo must be stored in a secure location. Accountability for this is the responsibility of the Investigator or qualified site staff. More details concerning this responsibility are included in Section 11.2.1.

Montelukast and placebo must only be dispensed by a Pharmacist or appropriately trained staff and only to subjects participating in this study. Once montelukast or placebo is dispensed to a subject, it can only be taken by that subject.

Additionally, Investigators should manage the treatment of subjects in compliance with the prevailing product label for montelukast treatment and ensure that subjects are fully informed about the potential risks and benefits of their treatments.

11.2.1. Montelukast and Placebo Accountability

The study site must maintain accurate records demonstrating dates and amounts of montelukast and placebo treatment received, to whom dispensed (subject-by-subject accounting), amount returned by subject, and accounts of any montelukast or placebo accidentally or deliberately destroyed. Subjects are to be instructed to return all montelukast and placebo kits, both used and unused, to the site. Unless otherwise notified, all montelukast and placebo kits, both used and unused, must be saved for study treatment accountability. At the end of the study, reconciliation must be made between the amount of montelukast and placebo supplied and dispensed; after reconciliation, montelukast and placebo will be destroyed at the study site or returned to Biogen. A written explanation must be provided for any discrepancies.

12. WITHDRAWAL OF SUBJECTS FROM STUDY TREATMENT **AND/OR THE STUDY**

A subject *must* permanently discontinue study treatment and be withdrawn from the study for any of the following reasons:

- Failure to meet the required eDiary compliance criteria (\geq 75%) in the 14 days prior to randomization.
- Failure to meet the GSRS score criteria during the DMF-GI Monitoring Period. •
- The subject experiences a medical emergency that necessitates permanent discontinuation of study treatment.
- The subject uses prohibited concomitant medications (as outlined in Sections 1 and 10.3.1).
- The subject withdraws consent.

Protocol 109MS414

- At the discretion of the Investigator for medical reasons or for noncompliance.
- The subject has a concurrent illness or injury, or abuses alcohol or drugs to the extent that, in the judgment of the Investigator and/or Sponsor, it would affect assessments of clinical status to a significant degree.

The reason for discontinuation of study treatment and withdrawal from the study must be recorded in the subject's CRF.

Subjects who discontinue study treatment will be withdrawn from the study. Whenever possible, subjects who prematurely discontinue study treatment should complete an ET Visit (undergoing the same assessments as the Week 10 Visit).

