6.2.2. Secondary Endpoints

The secondary endpoints of this study are as follows:

- Average change of GI severity scores from Day 0 to Day 10 as measured by total change of GSRS scores from Day 0 over the first 10 days (Day 1 to Day 10) divided by total number of days with GSRS recorded
- Average change of GI severity scores from Day 0 to Week 10 as measured by total changes of GSRS score from Day 0 over the first 10 weeks (Day 1 to Week 10) divided by total number of days with GSRS recorded
- Time to first worsening of GSRS in GI severity
- Time to recovery to Day 0 GSRS score from the last occurrence of the worst score in GI severity
- Average change of GSRS score from Day 0 score to Weeks 1, 2, 3, 4, 5, 6, and 8
- Average change of GSRS score from Day 0 to 72 hours from the initiation of randomized study treatment
- Proportion of subjects who require GI symptomatic therapy during the study
- Percentage of subjects who discontinue DMF therapy due to GI-related events from Day 0 to Week 10
- Proportion of subjects who experience flushing events

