6 SAMPLE SIZE JUSTIFICATION

Assuming that 40% of the placebo subjects will be improving (by chance) without any intervention, a total sample size of 118 (dosed with randomized study treatment), 59 per treatment arm (after randomization), would provide approximately 80% power to detect a 30% difference between the treatment arm and placebo arm in proportion of subjects with any improvement in GI severity, as measured by the average change from Day 0 in GSRS score to Day 10. Power was estimated assuming a 15% early discontinuation rate.

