7 STATISTICAL ANALYSIS METHODS

The statistical software, SAS[®], will be used for all summaries and statistical analyses.

Summary statistics will be used throughout. For continuous endpoints, the summary statistics will generally include: the number of subjects with data, mean, standard deviation (SD), median, 25th and 75th percentile (Q1, Q3), minimum and maximum. For categorical endpoints, the summary statistics will generally include: number of patients randomized and dosed, the number of patients with data, and the number and percent of subjects with data in each category.

All statistical tests will be 2-sided with a type I error rate of 5%, unless otherwise specified.

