7.2.2 Accounting of Subjects

The following subject categories will be summarized for this study using numbers and percentages based on all patients enrolled in the study:

- Number of subjects randomized
- Number of subjects who were dosed with DMF (DMF safety analysis population)
- Number of subjects dosed with study treatment (modified ITT population, Montelukast/placebo safety analysis population)
- Number of subjects completed study treatment
- Number of subjects discontinued study treatment
 - Reason for study treatment discontinuation
- Number of subjects continuing DMF at the Week 10 visit
- Number of subjects discontinued DMF by Week 10 or at Week 10
 - Reason for DMF treatment discontinuation
- Number of subjects completed the study
- Number of subjects withdraw from the study
 - Reason for study withdrawal

Subjects who discontinued treatment or withdrew from the study and the reasons for discontinuation or withdrawal will be listed. In certain cases, case report form (CRF) text detailing the reasons for discontinuation may suggest additional clarification of the reason provided on the CRF. Therefore, additional information for subject accounting may be presented, utilizing reasons for discontinuing treatment from the study reclassified based on the detailed CRF text.

7.2.3 **Protocol Deviations**

Protocol deviations identified in the study will be listed.

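### Protocol Section 12 ends the daily GSRS diary when study treatment stops, so follow-up to Week 10 is cut short for partly symptom-driven reasons that the SAP does not address

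*Combined protocol and SAP*

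**What the plan says.** Protocol Section 12 lists reasons for permanent discontinuation and then states: "Subjects who discontinue study treatment will be withdrawn from the study". It asks for an Early Termination (ET) visit where possible and for the reason to be recorded in the CRF. One listed reason is use of a prohibited concomitant medication. Sections 10.3.1 and 10.3.2 prohibit GI symptomatic therapy before Day 10.

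Footnotes to the protocol's schedule of events (Section 4.2) have the eDiary returned when the subject completes or discontinues the study. Otherwise entries are daily up to Week 10. After withdrawal there remains a safety telephone interview two weeks after the ET visit. Section 7.1 does not allow replacement once randomized treatment has begun.

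Endpoints that need data beyond the stop include the average GSRS change to Day 10 and to Week 10 and, in Protocol 6.2.2, "Percentage of subjects who discontinue DMF therapy due to GI-related events from Day 0 to Week 10". SAP 7.2.2 also plans to report "Number of subjects continuing DMF at the Week 10 visit", and it lists tablet discontinuation, DMF discontinuation and study withdrawal as separate categories.

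The term *study treatment* is not used consistently. The protocol synopsis names it as DMF. SAP 7.1.1 and 7.2.7 define it as montelukast or placebo.

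**The concern.** Stopping treatment and leaving the study are different events. Section 12 merges them, so diary days after a stop are missing because of the stop. Some stops will be for consent withdrawal or noncompliance. But a subject whose GI symptoms lead to a prohibited remedy in the first days must also leave, and that route ties missing GSRS scores to the outcome itself.

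If such stops differ between arms, or are equally frequent but concentrated among subjects who worsen, the comparison of arms is biased. Days that were never recorded cannot be recovered later. The double meaning of *study treatment* adds to this: a site cannot tell from Section 12 whether stopping only the tablet, or only DMF, requires withdrawal.

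**Working it through.** **1. Which endpoints lose data**

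- *Week 10 GSRS endpoints:* every early stop removes all later days. These are the most affected.
- *Day 10 primary endpoint (SAP 7.3.3):* only stops before Day 10 matter. A subject with at least one score in Day 1–10 stays in the modified ITT population (SAP 7.1.1) and is classified from the recorded days, with weight equal to the proportion of days recorded. A subject with no score drops out of the population.
- *DMF discontinuation to Week 10 (SAP 7.3.4):* a GI-driven DMF stop that is itself the withdrawal event is captured, because the reason goes in the CRF (Section 12) and GI events leading to discontinuation must be recorded (Section 15.2.1). The gap is a subject withdrawn for another reason who later stops DMF for a GI event. The SAP gives no rule for such subjects.

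**2. What the plan allowed for**

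Inputs from SAP 6 and 7: "Assuming that 40% of the placebo subjects will be improving (by chance) without any intervention"; the sample "would provide approximately 80% power to detect a 30% difference between the treatment arm and placebo arm" of 30 points (taken as 40% versus 70%); two-sided 5%; and "Power was estimated assuming a 15% early discontinuation rate".

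- Uncorrected: n = [1.96·√(2·0.55·0.45) + 0.842·√(0.4·0.6 + 0.7·0.3)]² / 0.30² ≈ 42 per arm.
- With continuity correction: 49 per arm.
- Inflated for discontinuation: 49 / 0.85 = 57.6, so 58 per arm or 116 in total, against 118 stated.

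The planned size is reproduced to within 2 subjects. The plan therefore already pays for 15% loss in numbers. What it does not cover is bias.

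**3. How many subjects**

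- Planned size: 0.15 × 118 = 17.7, about 18.
- At the enrollment closure in SAP 5 (about 60 dosed): 0.15 × 60 = 9.
- Week 10 endpoints: if stops were spread evenly over ten weeks (an assumption), each stopper would lose half the period on average, so about 0.15 × ½ = 7.5% of planned diary days would be missing, all of them after a stop.

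**4. Range for one arm's Day 10 worsening rate, at 30 per arm**

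The documents give no period for the 15%, so a range is needed.

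- Low end, stops spread evenly over 70 days: 9 × 10/70 = 1.3 of 60 stop by Day 10, or 0.64 of 30, about 2 points.
- Ceiling, all 15% stop before Day 10 and all are misclassified the same way: 4/30 = 13 points to 5/30 = 17 points.

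**5. Direction**

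This is an illustration on assumptions that are not in the documents: true worsening is 60% on placebo and 30% on montelukast (odds ratio 0.286), every early stopper is a worsener, and all stop after Day 3, so weight w = 0.3. With stopping fraction d, the weighted rate is (p − d + w·d) / (1 − d + w·d).

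| Stopping, placebo / montelukast | Estimated worsening | Odds ratio |
|---|---|---|
| 15% / 15% | 55.3% / 21.8% | 0.225 |
| 20% / 10% | 53.5% / 24.7% | 0.286 |
| 25% / 5% | 51.5% / 27.5% | 0.356 |

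First row, placebo: (0.60 − 0.15 + 0.045) / (0.85 + 0.045) = 0.495 / 0.895 = 55.3%. Worsening is too low in both arms in every row. The treatment effect is overstated, unchanged or understated depending on the split between arms.

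**The case against.** The strongest reply is that the loss is smaller than it looks and the SAP already does something about it. Most of this is fair as to size:

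- For Day 10, a poor tolerator whose recorded scores average above baseline is still classed as worsened. The outcome is kept but down-weighted, and that comes from the SAP weight rather than from Section 12.
- The repeated-measures model uses all recorded scores, and time to first worsening and time to recovery are censored at tablet stop.
- If *study treatment* means DMF, the sentence in Section 12 does not withdraw a subject who stops only the tablet.
- Continuing the diary is not neutral. SAP 7.3.3 averages over every recorded day, so scores after a DMF stop would enter the primary endpoint and could turn a subject who quit because of symptoms into an improver.

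The SAP methods still do not answer the point. The weight treats a symptom-driven stop exactly like a forgotten entry. The repeated-measures model assumes that a stopper's unrecorded scores would follow those of comparable subjects still recording, and censoring makes a similar assumption. The compliance subset in SAP Table 14 (at least 80% diary compliance, 5 tablet doses and 10 DMF doses) removes early stoppers altogether. No analysis tests informative dropout. The last objection is right and shapes the fix.

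A reader might also infer three stronger things that the documents do not support:

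- That the SAP counts withdrawn subjects as not having stopped DMF. It gives no rule either way.
- That the DMF-discontinuation endpoint loses the worst tolerators. A GI-driven DMF stop that triggers withdrawal is captured.
- That truncated subjects outnumber expected DMF discontinuations by about 3 to 1. This sets 15% against the figure of at most 5% in Protocol 5.2, which comes from pooled Phase 2 and 3 subjects. Here only subjects who reach a GI threshold are dosed (about 118 of 295), and the two groups may overlap.

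**Conclusion.** The concern holds as a data-collection weakness, mainly for the Day 1 to Week 10 GSRS endpoints. About 9 of 60 subjects (18 of 118) could be truncated if the plan's 15% applies. For the primary endpoint the shift in one arm's worsening rate lies between about 2 points, on even accrual, and a ceiling of 13 to 17 points that needs every stop before Day 10 and every misclassification in one direction. The ceiling should not be read as the expected size. The direction of bias in the treatment effect cannot be stated in advance.

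That the loss is partly driven by GI symptoms follows from the pre-Day 10 withdrawal route. How large that part is, the documents do not say. The planned sample size is not in question. Separately, the protocol synopsis, Protocol Section 12 and SAP 7.1.1, 7.2.2 and 7.2.7 must be reconciled on what *study treatment* means.

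**What to change.** *Protocol Section 12.* Record tablet stop, DMF stop and study withdrawal as three separate events, and say in each sentence which treatment is meant. Unless consent is withdrawn, continue eDiary entries to Week 10 (at minimum to Day 10), and obtain DMF status and the reason for any stop by telephone at Week 10. Amend the eDiary-return footnote to match.

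*SAP 7.3.3 and 7.3.4.* Flag GSRS scores recorded after a tablet or DMF stop, state whether they enter the primary average, and report the analysis with and without them. State how subjects whose DMF status at Week 10 is unknown are handled in the DMF-discontinuation proportion.

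*Cost.* The changes need a short protocol amendment, a few SAP sentences and one extra sensitivity analysis. The device and schedule already exist: randomized treatment ends at Week 8 while diary entries run to Week 10, so off-tablet diary collection is already part of the plan. Some stoppers will decline to continue, and a few more diary weeks must be tracked. No rule on when treatment is stopped is changed.

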13. EFFICACY ASSESSMENTS

13.1. Clinical Efficacy Assessments

The following efficacy assessments will be performed at multiple timepoints between the Randomization Visit and Week 10/ET Visit:

- GSRS scores
- Use of symptomatic GI therapy
- Occurrence and frequency of discontinuations from DMF therapy due to GI-related events
- Occurrence and frequency of flushing events

A numerical scale from 0 to 6 will be used for the GSRS scores as follows:

- No discomfort at all = 0
- Minor discomfort = 1
- Mild discomfort = 2
- Moderate discomfort = 3
- Moderately severe discomfort = 4
- Severe discomfort = 5
- Very severe discomfort = 6

Refer to Section 4.2 for the timing of assessments.

13.2. Exploratory Assessments

13.3. Future Biomarker and Genetic Assessments (Optional)

In subjects who provide additional consent, serum, RNA, and DNA samples may be collected for future biomarker/genetic analysis. Subjects will sign a separate, written ICF if they opt for their sample to be collected and used in this way.

The samples collected from the substudy may be utilized to identify or verify putative prognostic and predictive markers associated with disease and markers of therapeutic response to DMF

CONFIDENTIAL

treatment. Background and dynamic (on-study) clinical disease characteristics and associated biomarker data will be utilized to predict subsequent disease worsening (severity), identify high-risk patient subgroups, and identify predictors of response to DMF treatment.

Refer to Section 4.2 for the timing of assessments.

14. SAFETY ASSESSMENTS

14.1. Clinical Safety Assessments

The following clinical assessments will be performed at multiple timepoints between the Screening Visit and Week 12/ET Visit:

- AEs
- SAEs

Refer to Section 4.2 for the timing of assessments.

15. SAFETY DEFINITIONS, MONITORING, AND REPORTING

Throughout the course of the study, every effort must be made to remain alert to possible AEs. If an AE occurs, the first concern should be for the safety of the subject. If necessary, appropriate medical intervention should be provided.

At the signing of the ICF, each subject must be given the names and telephone numbers of study site staff for reporting AEs and medical emergencies.

15.1. Definitions

15.1.1. Adverse Event

An AE is any untoward medical occurrence in a patient or clinical investigation subject administered a pharmaceutical product and that does not necessarily have a causal relationship with this treatment. An AE can therefore be any unfavorable and unintended sign (including an abnormal laboratory finding), symptom, or disease temporally associated with the use of a medicinal product, whether or not related to the medicinal product.

15.1.2. Serious Adverse Event

An SAE is any untoward medical occurrence that at any dose:

- results in death
- in the view of the Investigator, places the subject at immediate risk of death (a life-threatening event); however, this does not include an event that, had it occurred in a more severe form, might have caused death
- requires inpatient hospitalization or prolongation of existing hospitalization
- results in persistent or significant disability/incapacity, or
- results in a congenital anomaly/birth defect.

An SAE may also be any other medically important event that, in the opinion of the Investigator, may jeopardize the subject or may require intervention to prevent one of the other outcomes listed in the definition above. (Examples of such medical events include allergic bronchospasm requiring intensive treatment in an emergency room or convulsions occurring at home that do not require an inpatient hospitalization.)

15.2. Monitoring and Recording Events

15.2.1. Adverse Events

Any non-SAE (including flushing) experienced by the subject between the time of first dose of study treatment and the Safety Follow-up Telephone Interview is to be recorded on the CRF, regardless of the severity of the event or its relationship to study treatment.

There are 2 exceptions to this:

CONFIDENTIAL

- Any GI-related AE experienced by the subject between the time of the first dose of DMF and study completion is to be recorded by the subject in his/her eDiary. Any GI AEs that lead to permanent study discontinuation or withdrawal or are serious must be recorded.
- Non-SAEs of MS relapse will not be collected unless leading to permanent treatment discontinuation or study withdrawal.

Nonserious GI AEs should be recorded in the eDiary and not in the eCRF.

For subjects who permanently discontinue DMF during the study, AEs should be recorded through the Safety Follow-Up Telephone Interview conducted 2 weeks (±5 days) after the subjects' Final Clinic Visit.

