4.2. Schedule of Events

Table 1:Schedule of Events

Assessment	Screening Visit ^a	Screening Period (2 Weeks +14 Days)	Randomization Visit ^a (Week -4)	DMF-GI Monitoring Period (up to 28 Days)	Wk 0 ^{a,b}	Wk 2 ^c	Wk 4 ^a	Wk 8 ^c	Wk 10 ^a /ET	Safety Follow- Up ^d (± 5 days)
Clinic Visit	Х		х		Х	х	х	Х	Х	
Informed Consent	Х									
Eligibility Criteria	Х		X ^e							
Demographics	Х									
Vital signs ^f	Х									
Medical History (incl. MS disease status) ^g	Х									
Alcohol Consumption	Х									
Tobacco Use	Х									
Pregnancy Testing ^h	Х		х							
Concomitant Medications/ Procedures	Х		х		х	х	х	х	х	Х
Blood Biomarkers (optional) ^j			х				Х		Х	
Dispense eDiary	Х									
eDiary Training	Х									
eDiary Entries (Daily) ^k										
Return eDiary to Clinical ^l			X ^m	X ^m					х	

Version 3

Protocol 109MS414 Phase 4 Study of GI Tolerability in DMF-Treated Subjects With Relapsing Forms of MS

Assessment	Screening Visit ^a	Screening Period (2 Weeks +14 Days)	Randomization Visit ^a (Week -4)	DMF-GI Monitoring Period (up to 28 Days)	Wk 0 ^{a,b}	Wk 2 ^c	Wk 4 ^a	Wk 8 ^c	Wk 10ª/ET	Safety Follow- Up ^d (± 5 days)
Dispense DMF With Dosing Instructions			Х							
DMF Administration (Daily)			DMF administration will occur every day as per the USPI							
Randomization			Х							
Dispense Randomized Study Treatments			X ⁿ							
Randomized Study Treatment Administration (Daily)					Randomized study treatment administration will occur every day as per the prescribing information.					
SAEs	SAE data will be collected from the signing of the informed consent up to the Safety Follow-Up Telephone Interview. MS relapses resulting in hospitalization are considered SAEs but will not be reported as SAEs in the study unless the relapse is complicated by other SAEs or is fatal.									
AEs				AE data will be collected from the first dose of DMF up to the Safety Follow-Up Telephone Interview.						

Note: Weeks 2, 4, and 8 will have a visit window of ± 2 days, and Week 10 will have a visit window of ± 3 days.

Abbreviations: AE = adverse event; DMF = dimethyl fumarate; DNA = deoxyribonucleic acid; eDiary = electronic diary; EDSS = Expanded Disability Status Scale; ET = early termination; GI = gastrointestinal; GSRS = Gastrointestinal Symptom Rating Scale; (Compared to the state of th

; MS = multiple sclerosis; ; RNA = ribonucleic acid; SAE = serious adverse event; USPI = United States Prescribing

Information;Wk = week.

^a This visit must be performed in clinic.

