^b Subjects will receive an alert through the eDiary if their GSRS scores reach the appropriate threshold. This alert will tell the subject to begin taking the randomized study treatment the same day. At this time, study site should arrange the Week 0 Visit as soon as possible after the first administration of randomized study treatment. Visit dates will be measured from the first administration of randomized study treatment.

^c This visit may be performed remotely if more convenient for the subject; site must telephone the subject to document concomitant medications/procedures and AEs.

^d The safety follow-up will be performed as a telephone interview 2 weeks (±5 days) after the Week 10/ET visit.

^e GI symptom and eDiary compliance assessment.

^f Including height and weight measurements and vital signs (temperature, blood pressure, and sitting blood pressure).

^g Medical history, including MS disease status, will include collection of information on duration of MS, relapse history, EDSS score, and treatment for MS.

^h Dipstick test (only for women of childbearing potential).

CONFIDENTIAL

^j Serum, RNA, and DNA samples will be collected for biomarker analysis and future use analysis in subjects who provide additional consent. A single DNA sample can be taken at any of prespecified timepoints.

Version 3

^k Subjects will be required to record their daily GI symptoms in the eDiary every day from the Screening Visit up to Week 10.

¹ eDiaries will be returned if (1) the subject fails during the Screening Period, (2) the subject does not reach the required GI symptom threshold during the DMF-GI Monitoring Period, or (3) the subject completes or discontinues the study.

^m Subjects who do not reach the GI symptom threshold during the DMF-GI Monitoring Period (a GSRS score of ≥ 5 in 1 question for 1 day, ≥ 4 in 1 question for 2 consecutive days, or ≥ 3 in 1 question for 3 consecutive days) will be discontinued.

ⁿ Subjects are dispensed randomized study treatment at this visit but must not begin taking the medication until alerted about their eDiary.

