5.2. Study Rationale

Two large Phase 3 studies and 1 Phase 2 study of DMF in subjects with RRMS demonstrated substantial benefits over placebo across a range of clinical and radiologic measures of disease activity (Phase 3 Study 109MS301 [DEFINE], Phase 3 Study 109MS302 [CONFIRM], and Phase 2 Study C-1900). While the overall safety profile was favorable in these studies, the incidence of AEs associated with GI tolerability, including diarrhea, nausea, abdominal pain, vomiting, and dyspepsia, was increased in DMF-treated subjects compared with those who received placebo. Between 27% and 38% of all DMF-treated subjects in the 3 studies experienced GI events within the first 3 months of treatment, and whereas 11% to 16% of subjects used GI-related symptomatic therapies, it was unclear whether these were taken in response to a GI-related AE that occurred in conjunction with dosing or if the therapy was effective. The incidence of these events was higher during the first month of treatment and decreased in the second and subsequent months of treatment. The majority of subjects reported these AEs to be of mild to moderate severity. Nevertheless, study discontinuations due to GI events were increased in DMF-treated subjects (\leq 5%) compared with placebo-treated subjects $(\leq 2\%)$, pooled Phase 2 and Phase 3 subjects). In addition, a recently completed single-arm, open-label, Phase 4 Study (109MS403 [MANAGE]) as well as a placebo-controlled study of Pepto-Bismol[®] (bismuth subsalicylate) on GI tolerability (Study 109HV110 [PREVENT]) showed similar results in terms of time course, severity, and incidence of GI events. Histopathology from biopsies taken from a subset of subjects in PREVENT suggested some evidence of GI mucosal eosinophil infiltration. In an independent, open-label, 30-day study (21 subjects) investigating the effect of montelukast in DMF-related GI symptoms, GI symptoms were significantly attenuated in the majority of subjects; GSRS scores decreased on average by 81% within 72 hours [Tornatore and Amjad 2014]. The effect of montelukast may suggest that the pathogenesis of the GI symptoms with DMF could be due to a local immunomodulatory effect of DMF. Montelukast is an approved product for asthma with a well-established safety profile [[SINGULAIR® USPI 2014]]. If a larger randomized, controlled study could demonstrate a benefit on decreasing the known GI tolerability events during initiation of therapy, it would be a clear benefit for subjects choosing DMF to treat MS who experience GI side effects.

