15.6. Investigator Responsibilities

The Investigator's responsibilities include the following:

- Monitor and record all AEs, including SAEs, regardless of the severity or relationship to study treatment.
- Determine the seriousness, relationship, and severity of each event.
- Determine the onset and resolution dates of each event.
- Monitor and record all pregnancies and follow-up on the outcome of the pregnancy.
- Complete an SAE Form for each serious event and fax it to within 24 hours of the study site staff becoming aware of the event.
- Pursue SAE follow-up information actively and persistently. Follow-up information must be reported to within 24 hours of the study site staff becoming aware of new information.

CONFIDENTIAL

- Ensure all AE and SAE reports are supported by documentation in the subjects' medical records.
- Report SAEs to local IRBs, as required by local law.

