7.4.2 Analysis Methods

Safety analyses will summarize all adverse events (AEs). In general, SAE and AEs will be analyzed based on incidence, defined as the proportion of subjects who had at least one occurrence of an event out of the number of subjects in the safety population.

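### Tables titled as the incidence of adverse events would omit non-serious GI events kept only in the eDiary, and Protocol 15.2.1 is inconsistent about which GI events go in the eCRF

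*Combined protocol and SAP*

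**What the plan says.** **Recording.** Protocol 15.2.1 sends non-serious adverse events to the CRF up to the safety telephone call and then makes an exception for GI events: "Any GI-related AE experienced by the subject between the time of the first dose of DMF and study completion is to be recorded". The place it names for this is the subject's own diary. It continues: "Any GI AEs that lead to permanent study discontinuation or withdrawal or are serious must be recorded". A separate sentence then says "Nonserious GI AEs should be recorded in the eDiary and not in the eCRF".

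**Timing.** The schedule of events (Protocol 4.2) says "AE data will be collected from the first dose of DMF up to the Safety Follow-Up Telephone Interview". For the diary it says "Subjects will be required to record their daily GI symptoms in the eDiary every day from the Screening Visit up to Week 10". The device is returned when the subject completes or leaves the study. The call follows two weeks (±5 days) after Week 10 or early termination, and Protocol 7.2.6 has it ask about any adverse events.

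**Assessment and reporting.** Protocol 15.2.3 requires seriousness, relationship and severity for every event. Protocol 15.6 tells the investigator to "Monitor and record all AEs, including SAEs, regardless of the severity or relationship to study treatment", with onset and resolution dates. Protocol 16.5.2 promises incidence of all events by system organ class and preferred term, and by severity and relationship. SAP 7.4.2 likewise covers all adverse events. Tables 33.1 and 33.2 (incidence), 37 (by severity) and 38 (by relationship) carry no exclusion in their titles.

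**The concern.** GI tolerability is the risk this trial was set up to study. If most non-serious GI events never reach the adverse event database, tables that read as complete will understate GI incidence. A reader who sets them beside the earlier DMF studies, where GI events were counted as adverse events, would conclude wrongly that GI events were uncommon here. A GI effect of montelukast itself would also be missing from the adverse event tables unless it was serious or led to discontinuation.

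The conflict inside 15.2.1 touches a secondary endpoint, DMF discontinuation due to GI-related adverse events. A site that follows the last of the three sentences would leave out of the eCRF the events that explain those discontinuations.

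**Working it through.** The plan states no figure for this point, so there is none to reproduce. The check has a textual part and an illustration of size.

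**1. Is there a route from diary to table?** SAP 7.4.2.1 describes MedDRA coding without mentioning the eDiary. SAP 7.2.8 does deal with a split source for concomitant medication (GI in the diary, non-GI in the CRF), but nothing equivalent exists for adverse events. No section has diary entries coded, graded or assessed for causality. The GI rows of Tables 33, 37 and 38 can therefore draw only on events that 15.2.1 requires to be recorded outside the diary.

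**2. Do the efficacy tables fill the gap?** SAP Tables 15.1, 16 and 18 give average change in GSRS by arm, overall and by dimension, in dosed subjects. They do not give the number of subjects with each symptom. Of the 295 planned for randomization, 295 − 118 = 177 would never start montelukast or placebo. The SAP's modified ITT population (7.1.1) excludes them, but those who took DMF belong to the DMF safety population used in Tables 33.2, 37 and 38.

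**3. Size.** Inputs:
- Historical GI event rate, Protocol 5.2: "Between 27% and 38% of all DMF-treated subjects in the 3 studies experienced GI events within the first 3 months of treatment".
- Historical discontinuation for GI events on DMF, Protocol 5.2: at most 5%.
- Assumed early discontinuation from any cause, Protocol 16.7: 15%.
- Dosed subjects: about 60 when enrollment closes (SAP 5); 118 in the original plan, from 295 randomized.

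Subjects = rate × N:

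| N | GI event, 27% to 38% | GI discontinuation, 5% | All 15% GI-related |
|---|---|---|---|
| 60 dosed | 16.2 to 22.8 | 3.0 | 9.0 |
| 118 dosed | 31.9 to 44.8 | 5.9 | 17.7 |
| 295 on DMF | 79.7 to 112.1 | 14.8 | not applied |

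Share of GI-affected subjects missing from the GI rows, at N = 60:
- At 5%: (16.2 − 3.0)/16.2 = 81%, to (22.8 − 3.0)/22.8 = 87%.
- At 15%: (16.2 − 9.0)/16.2 = 44%, to (22.8 − 9.0)/22.8 = 61%.

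Serious GI events that did not cause discontinuation would add to the recorded count; the documents give no rate for them. Every dosed subject has already met a GI symptom threshold, so the true number with GI events is probably above 16 to 23.

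**4. Between diary return and the call.** The interval is 14 − 5 = 9 to 14 + 5 = 19 days after Week 10 or early termination. The diary exception ends at study completion, which is not defined. If that means Week 10 or early termination, the general CRF rule resumes. If it means the call, or if the undated sentence barring the eCRF governs, a site could read the rule as forbidding entry when the subject no longer has a diary.

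**The case against.** The strongest reply is that GI symptoms are the best-measured data in the trial. They are recorded daily, form the primary endpoint and are compared by arm through Week 10, so a montelukast effect on GSRS symptoms could show there. The rule on where to record an event also does not cancel the investigator's duty to assess it. Both points stand. They limit the harm, but they do not supply incidence by symptom or make the table titles accurate. Similarly, Protocol 12 puts the reason for discontinuation in the CRF, so the discontinuation endpoint is not lost. What is uncertain is the adverse event record behind it.

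A reader might infer more than the documents support:

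- **That GI events after diary return have nowhere to go.** The call collects any adverse events, and on one natural reading the CRF rule resumes when the diary is returned. The text is ambiguous, not silent.
- **That vomiting cannot be recorded.** It is a named DMF event and is not among the GSRS items printed in SAP 7.3.2. However, the diary is described broadly and never limited to the 15 GSRS items, and 15.2.1 tells subjects to enter any GI-related event in it. The printed diarrhea dimension also repeats two constipation items, so only 13 of the 15 items can be read. The gap is possible, not proven.
- **That the tables will show almost no GI events, with 5% as a ceiling.** The 5% comes from earlier subjects who were not selected for GI symptoms. Dosed subjects here are selected for them, so 5% is not a bound.

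**Conclusion.** The point holds as a reporting and recording defect. It does not threaten the primary analysis. As written, the GI rows of Tables 33, 37 and 38 would contain only serious events and those leading to discontinuation or withdrawal. With about 60 dosed subjects, that is some 3 to 9 against 16 to 23 expected with a GI event, so between 44% and 87% of affected subjects would be missing. These figures assume that the historical rates carry over; the upper count of 9 further assumes that every early discontinuation is GI-related. They illustrate the size and are not a forecast.

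Separately, two sentences in 15.2.1 conflict over non-serious GI events that cause discontinuation, and recording in the 9 to 19 days before the safety call is unclear because study completion is undefined.

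**What to change.** **SAP 7.4.2.1 and Section 8.** State in the titles of Tables 33 to 38 that non-serious GI events recorded only in the eDiary are excluded; this matters most for 33, 37 and 38. Add a companion table by arm, from diary data already collected, for each safety population:

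- *Montelukast/placebo population:* subjects with any GSRS item reaching 3 or more and above its Day 0 score after the first dose, by item.
- *DMF population:* subjects with any item above its highest Screening Period score, by item and maximum grade. A cut-off of 3 would not serve here: under Protocol 7.2.4 one such day is itself the dosing trigger, so the table would mostly restate who was dosed.

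A footnote should say that these are symptom scores, without MedDRA terms or causality.

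**Protocol 15.2.1.**
- Reconcile the two sentences so that non-serious GI events leading to discontinuation of DMF, of randomized treatment or of the study go in the eCRF.
- State that the diary exception ends when the diary is returned, so that later GI events, including those reported at the safety call, go in the eCRF.
- Send to the eCRF any GI event for which the diary has no field. Vomiting may be one; check the diary specification.

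**Cost.** Two extra tables and slightly more site data entry. The SAP changes remain possible after enrollment closes.
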